#### 4.3.2. Analysis Methods

The secondary efficacy endpoints will be analyzed for both the eITT and fITT analysis sets.

For all continuous secondary efficacy endpoints, descriptive statistics of actual values and mean changes from baseline at each scheduled time point will be provided by treatment group for the lead-in period, the double-blind treatment period and the withdrawal period. A mean-SE plot over time will be presented for observed values during the lead-in period, the double-blind treatment period and the withdrawal period by treatment group.

For each of the continuous secondary efficacy endpoints, the JNJ-42165279 treatment group will be compared to placebo using the same MMRM model as for the HDRS17 total score.

To explore the results for the subgroup of placebo responders, descriptive statistics of actual values and mean changes from baseline for the continuous secondary endpoints at each scheduled time point will be provided by treatment group for the lead-in period, the double-blind treatment period and the withdrawal period for the fITT subset of placebo responders. Mean-SE plots over time will also be presented for this subgroup.

Frequency tables and figures for the categorical secondary efficacy endpoints will be provided at each scheduled time point by treatment group for the lead-in period, the double-blind treatment period and the withdrawal period. Chi square test will be used to test the overall differences between the treatment groups at week 6 of the double-blind treatment period. If deemed appropriate, Cochran–Mantel–Haenszel test with (pooled) center as stratification factor will be performed.

A cumulative distribution plot of the percent reduction in HDRS17 total score from double-blind treatment baseline at Week 6 of the double-blind treatment period will be provided. A similar plot will be provided for the SIGH-A total score percent reduction.

#### 4.4. Patient Reported Outcomes

##### 4.4.1. Definitions

- **Clinically Useful Depression Outcome Scale (CUDOS-A):** The CUDOS contains 18 items assessing all of the Diagnostic and Statistical Manual of Mental Disorders (5th edition) (DSM-5) inclusion criteria for major depressive disorder and dysthymic disorder as well as psychosocial impairment and quality of life. The 16 symptom items are rated on a 5-point Likert scale in order to keep the scale brief. The CUDOS was designed to be brief (completed in less than 3 minutes), quickly scored (in less than 15 seconds), clinically useful (fully covering the DSM-5 symptoms of major depressive disorder and dysthymic disorder), reliable, valid and sensitive to change. The content of the CUDOS-A subscale was based on the DSM-5 criteria for the anxious distress specifier. A CUDOS-A total score will be calculated as the sum of the 5 item scores, and ranges from 0 to 20, with higher scores indicates higher levels of anxious distress.
- **Cognitive and Physical Functioning Questionnaire (CPFQ):** The CPFQ is a brief self-report scale that provides additional information regarding the impact of adjunctive treatment on aspects of cognitive function including attention, memory and mental acuity. Subjects with MDD are often reported to have difficulties with functioning in this area. A CPFQ total score will be calculated as the sum of the 7 item scores, and ranges from 7 to 42, with higher scores indicating more difficulties with cognitive and physical functioning.
- **Snaith-Hamilton Pleasure Scale (SHAPS):** The SHAPS is a 14-item, self-report instrument developed for the assessment of hedonic capacity. The SHAPS was developed to minimize cultural, gender, and age biases in the evaluation of hedonic capacity. It not only measures hedonic tone, but also its absence, i.e. anhedonia. Anhedonia can be a core symptom of depression. Four major domains are covered in the scale, namely interest/pastimes, social interaction, sensory experience, and food/drink. Each of the SHAPS items has a set of four response categories: Strongly Disagree, Disagree, Agree and Strongly Agree, with either of the Agree responses receiving a score of 0 and either of the Disagree responses receiving a score of 1. A SHAPS total score will be calculated as the sum of the 14 item scores, and ranges from 0 to 14. A higher SHAPS total score indicates higher levels of present state of anhedonia.

- **Medical Outcomes Study Sleep-Revised (MOS Sleep-R):** Symptoms of poor sleep commonly occur in anxiety and mood disorders. The MOS Sleep-R is a subject-completed scale containing 12 items that addresses various dimensions of sleep. Ten items are answered on a 6-point scale, where 1=“all of the time” and 6=“none of the time”. One item on sleep latency is answered on a 5 point Likert scale from 1=“0-15 minutes” to 5=“more than 60 minutes”. One item on the duration of sleep allows the subject to write in the number of hours slept per night. The instrument yields six subscales: sleep disturbance, snoring, shortness of breath or headache, sleep adequacy, sleep somnolence, and sleep quantity. The version to be used in this study has a recall period of the 4 past weeks. Quantity of sleep is scored as the average number of hours slept per night. Other subscales scores are converted to a T-score with a mean of 50, standard deviation (SD) of 10 and range of 0 to 100, where higher scores indicate fewer sleep-related problems.
- **Perceived Stress Scale (PSS):** The PSS is the most widely used psychological instrument for measuring the perception of stress. It is a measure of the degree to which situations in one’s life are appraised as stressful. The questions in the PSS ask about feelings and thoughts during the last month. In each case, respondents are asked how often they felt a certain way (0 never, 1 almost never, 2 sometimes, 3 fairly often, 4 very often). A PSS total score is obtained by reversing responses (e.g. 0 4, 1 3, 2 2) to the 4 positively stated items (items 4, 5, 7 and 8) and then summing across all items. The PSS total score ranges from 0 to 40 with higher scores indicating higher severity of symptoms.
- **Self-Assessment of Treatment Experience (SATE):** The SATE questionnaire is a 4-item self-report scale designed to provide additional information regarding the subject’s subjective experience while taking the treatment.

#### 4.4.2. Analysis Methods

The patient reported outcome efficacy endpoints will be analyzed for both the eITT and fITT analysis sets.

For all continuous patient reported outcome efficacy endpoints, descriptive statistics of actual values and mean changes from baseline at each scheduled time point will be provided by treatment group for the lead-in period, the double-blind treatment period and the withdrawal period. A mean-SE plot over time will be presented for observed values during the lead-in period, the double-blind treatment period and the withdrawal period by treatment group.

Frequency tables and figures for the categorical patient reported outcome efficacy endpoints will be provided at each scheduled time point by treatment group for the lead-in period, the double-blind treatment period and the withdrawal period.

## 5. SAFETY

All safety analyses will be based on the Safety analysis set, except for the analysis of adverse events, that will also be performed for the enriched Safety analysis set.

All safety data will be listed for the All Subjects Set.

### 5.1. Imputation Rules for Missing AE Date/Time of Onset/Resolution

A conservative approach will be used to handle the missing dates for adverse events. The rules for estimating incomplete AE onset dates will be as follows:

- (1) The missing day of the month will be estimated as follows: If the month and year are known and double-blind study medication started during that month then the estimated date is the start date of double-blind study medication. If the month and year are known and double-blind study medication started prior to that month then the estimated date is the 1st day of the month. If the month and year are known and double-blind study medication started after the month, then no estimation will be done, and the AE will not be considered as treatment emergent for the double-blind phase.
- (2) If both the day and the month are missing: No estimation will be performed. However, these AEs will be considered treatment emergent for the double-blind phase and will be included in the double-blind treatment summaries, except for the calculation of duration of the AE. Attempts will be made to get at least the month for the adverse events.

The rules for estimating incomplete AE onset times will be as follows:

The missing times will be estimated as follows: use time 00:00:00 of the given/imputed date for the start date/time of an AE and use 23:59:59 for the end date/time of an AE.

For incomplete AE resolution dates, the rules are:

- (1) The missing day of the month will be estimated as follows: If the month and year are known and the study medication was stopped before, or during that month, the estimated date is the last day of the month or the end of the double-blind phase, whichever is earlier. If the study medication stopped after that month then the estimated date is the last day of the month.
- (2) If both the day and the month are missing: the estimated resolution date is the end of the double-blind phase.

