### 2.4. Analysis Timepoints and Phases

Please refer to the time and events schedule in the latest version of the protocol for analysis timepoints per assessment.

**Baseline (reference time point):** for each of the Lead-in, DB Treatment and Withdrawal Period, the reference assessment, i.e. baseline, is the measurement the closest, and prior to the first study medication administration of that period. The baseline measurement may be taken from a scheduled or unscheduled visit.

**End Point for double-blind treatment period:** end point is defined as the last non-missing post-baseline observation during the double-blind treatment period. End point will be defined only for the double-blind treatment period.

Analysis phases will be constructed as follows:

Analysis Phase	Start Date/time	End Date/time
Screening	00:00 of the date of signing the informed consent	1 minute before the first study medication administration in the Lead-in Period
Lead-in Treatment Period	Date/time of the first study medication administration in the Lead-in Treatment Period	1 minute before the first study medication administration in the Double-Blind Treatment Period

		If the subject does not enter the Double-blind Treatment Period then use 23:59 of the day before the date of the first Follow-Up visit
Double-Blind Treatment Period	Date/time of the first study medication administration in the Double-Blind Treatment Period  If the subject takes the morning dose on the day of randomization prior to the randomization (i.e. a dose of the lead-in medication), the time of morning intake of the next day is not known. The start date of the double-blind treatment period will be the day after the day of randomization, and the time of intake will be imputed as 0:00.	1 minute before the first study medication administration in the Withdrawal Treatment Period.  If the subject does not enter the Withdrawal Treatment Period then use 23:59 of the day before the start of the Follow-Up period.
Withdrawal Treatment Period	Date/time of the first study medication administration in the Withdrawal Period	Day 77 visit or early withdrawal visit for subjects who dropout early.
Follow-up	00:00 of the date after the Day 77 visit or early withdrawal visit for subjects who dropout early.	23:59 of the day of study termination (date of last contact)

The last phase, whichever it is for a subject, always ends on 23:59 of the day of study termination (last contact).

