### 5.2. Adverse Events

The verbatim terms used in the CRFs by the investigator to identify adverse events (AEs) will be coded using the current Medical Dictionary for Regulatory Activities (MedDRA) maintained by the sponsor.

Therapeutic reach is the number of days after the last dose intake that a subject is still considered to be potentially affected by study drug. For JNJ-42165279, therapeutic reach is defined as 4 days. AEs during the double-blind treatment period will be summarized using the therapeutic reach. Therapeutic reach will only be applied to the end of double-blind treatment period or to subjects who discontinue during the double-blind treatment period.

A treatment-emergent AE (TEAE) is an event that is new in onset or increased in severity following treatment initiation. Any event with a start date and time after the first dose intake will be considered treatment-emergent. An event that starts prior to and ends after the initiation of study medication will be considered treatment-emergent only if the severity increases after the start of medication. An event that starts in the withdrawal or follow up period but within the therapeutic reach of 4 days of the double-blind treatment period will be considered treatment-emergent during the double-blind treatment period. Adverse events with onset date during the withdrawal/follow-up period outside the therapeutic reach of 4 days will be summarized separately.

- The number (%) of subjects with TEAEs will be summarized by system organ class and preferred term for each treatment group and study period. A summary will be created for the most common TEAEs ( $\geq 5\%$  incidence in either treatment group). Both of these summaries will also be provided for the enriched Safety analysis set.
- In addition, TEAEs will be summarized by severity and relationship to study drug for each treatment group and study period by system organ class and preferred term. For the summaries of AEs by severity/relationship to study drug, the observation with the most severe occurrence/closest relationship to study drug will be chosen if there is more than one incident of an adverse event reported during the treatment phase by the subject.

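### SAP 5.1 puts an adverse event with no onset time at midnight, so when that day's first double-blind dose has a clock time the event is assigned to the placebo lead-in

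*SAP*

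**What the plan says.** Three sections of the SAP act together.

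- **SAP 5.1, intent.** "A conservative approach will be used to handle the missing dates for adverse events".
- **SAP 5.1, missing onset day.** If double-blind medication started in the known month of onset, "then the estimated date is the start date of double-blind study medication". If both day and month are missing, no date is estimated and the event is counted as treatment-emergent for the double-blind phase.
- **SAP 5.1, missing onset time.** The instruction is to "use time 00:00:00 of the given/imputed date for the start date/time of an AE". It covers recorded and imputed dates alike.
- **SAP 5.1, missing resolution day.** If study medication stopped before or during the month, "the estimated date is the last day of the month or the end of the double-blind phase, whichever is earlier". If the month is missing too, the end of that phase is used.
- **SAP 2.4, phases.** The double-blind treatment period starts at "Date/time of the first study medication administration in the Double-Blind Treatment Period", and the lead-in ends "1 minute before the first study medication administration in the Double-Blind Treatment Period". There is one exception, introduced by "If the subject takes the morning dose on the day of randomization prior to the randomization": the period then starts on the following day, with the intake time imputed as 0:00.
- **SAP 5.2, counting.** "Any event with a start date and time after the first dose intake will be considered treatment-emergent". An event that began earlier and continues past the start of medication counts only if its severity increases. Tables are by treatment group and study period, and all adverse events are listed.

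**The concern.** The date rule and the time rule in SAP 5.1 pull in opposite directions. Moving an event with a missing day to the double-blind start date makes sense only if the event is meant to count as double-blind. The time rule then sets it at midnight, which on a day with an actual dose time lies before the dose and so in the lead-in. An event with no date information beyond the year is counted as double-blind, while one whose month is known can be pushed out. The less complete record gets the more conservative treatment.

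Safety and tolerability are part of the primary objective (SAP 1.1), and the double-blind treatment-emergent tables are where the two arms are compared on drug. At the other end of the period, SAP 5.2 protects attribution with a therapeutic reach of 4 days. Nothing in SAP 5.1 or 5.2 does the same at the start.

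**Working it through.** The plan states no figure here to reproduce. The check applies the timestamp rules as written.

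**Rules used**
- Phase (SAP 2.4): double-blind if onset is at or after the double-blind start; lead-in if onset is at or before that start minus 1 minute.
- Double-blind treatment-emergent test (SAP 5.2, with the double-blind dose as reference): onset strictly later than the first dose.
- Missing time (SAP 5.1): onset = 00:00:00 on the recorded or imputed date.

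The clock times below are illustrative; the documents give none.

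| Double-blind start | Imputed onset | Phase assigned | Strictly after first dose? |
|---|---|---|---|
| Actual dose, 08:00 | 00:00 same day | Lead-in | No |
| Actual dose, 09:30 | 00:00 same day | Lead-in | No |
| Actual dose, 13:00 | 00:00 same day | Lead-in | No |
| Imputed, 0:00 on the day after randomization | 00:00 that day | Double-blind | No (tie) |

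An event with a missing day that is moved to the double-blind start date gives the same four rows, whatever day it really began. In the first three rows the event returns to the double-blind table only if its severity increases after the dose. In the fourth the phase is right, and only the strict wording of SAP 5.2 stands in the way.

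The first three rows are realistic. Protocol Section 6 has subjects take study medication on site, witnessed, at scheduled visits, and SAP Table 1 makes Visit 5 both the last lead-in visit and the double-blind baseline.

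With onset set to the later of 00:00 and the first double-blind dose time, all four rows give double-blind.

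**Date order (illustrative dates)**
- *Onset after resolution.* Double-blind medication starts 20 July, onset is recorded only as July, resolution is known to be 5 July. The onset is imputed as 20 July, 15 days after the event ended.
- *Resolution before onset.* The 6-week treatment period ends 1 July, so Day 77 falls 14 days later, on 15 July. Study medication stops in July and resolution is recorded only as July.
  - Withdrawal event, onset 10 July. If the capped phase is the 6-week period, resolution = min(31 July, 1 July) = 1 July, before onset. If the phase runs to Day 77, min(31 July, 15 July) = 15 July, which is in order.
  - Follow-up event, onset 20 July. Even on the longer reading, min(31 July, 15 July) = 15 July, before onset.

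**Size.** The number misassigned depends on how many adverse events lack an onset time or day and how many subjects have an actual rather than an imputed first-dose time. The documents give neither. Only the sensitivity of one table can be shown. With the planned 140 × 0.90 / 2 = 63 randomized per arm, 4/63 = 6.3% meets the 5% cut-off for common events in SAP 5.2 and 3/63 = 4.8% does not. One reassigned subject could therefore move a term across the line; this says nothing about whether any will be.

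**The case against.** The strongest reply is that the defect is narrow and nothing is lost. Much of that stands.

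- First-day events with a recorded time are classified correctly. A reader might infer that all events on the first drug day go to the lead-in; the text does not support that.
- An event without a time that truly began before the dose belongs in the lead-in, so not every such event is misassigned.
- Three groups escape: subjects under the 0:00 exception, events missing both day and month, and events that worsen after the dose.
- The event stays in the listings. If the first dose in SAP 5.2 means the first lead-in dose, it also remains treatment-emergent, but under the wrong period. Tables count subjects per term, so a subject with the same term again during double-blind treatment still counts.
- A reader might infer that a placebo column gains drug events. SAP 5.2 tabulates by treatment group and study period and specifies no pooled placebo column, so what is wrong is the period label.
- A reader might point to the rapid Phase 1 absorption as evidence that first-day events will be frequent. The peak times of 0.5 to 2.5 hours in Protocol Section 1.1 are for 100 mg, given as an oral suspension, whereas this trial gives 25 mg tablets after breakfast or a snack. No passage says that events clustered on the first day.
- The resolution cap depends on an undefined term. Protocol Section 10.1 ends the double-blind phase at Week 11, and Section 3.1 places withdrawal inside it. On that reading only follow-up events are affected. SAP 5.2 plans no summary of event duration, so the effect is mainly on listings.

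The reply does not remove the core. Under the general rule of SAP 2.4, the midnight onset falls before the dose and no other rule restores the event. Applying the same rule in both arms does not make the period assignment right.

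**Conclusion.** The point holds in a limited form. Where the first double-blind dose has an actual clock time, a missing-time event dated on that day, or a missing-day event moved to that date, is assigned to the placebo lead-in unless it later worsens. This contradicts the conservative approach that SAP 5.1 announces and can undercount double-blind treatment-emergent events in the tables by group and period. Under the 0:00 exception only a tie with the wording of SAP 5.2 remains.

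The size is unknown and cannot be derived from the documents. A reader might attach a count of subjects by assuming a first-day event rate; neither document gives such a rate, nor the frequency of missing times or of each dosing pattern.

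Separately, an imputed onset is not bounded by a known resolution, which can move an already resolved event into the double-blind period, the opposite direction of error. An imputed resolution can precede onset for follow-up events on any reading, and for withdrawal events too if the phase means the 6-week treatment period.

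**What to change.** - **SAP 5.1, onset time.** If the recorded or imputed onset date equals the date of the first double-blind dose and the time is missing, set onset to the time of that dose, unless recorded information, such as an earlier end date or time, shows onset before it.
- **SAP 5.2.** Count events that start at or after the first dose. Without this, an onset set equal to the dose time would still fail the test.
- **SAP 5.1, date order.** Require that an imputed onset is not later than a known resolution and that an imputed resolution is not earlier than onset.
- **SAP 5.1, terms.** Define the double-blind phase used in the resolution rule by reference to the phases in SAP 2.4.

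The cost is a few sentences and minor programming, with no new data. The trade-off is that a few events that truly began before the dose may be counted as double-blind, which is the direction a conservative rule should err.

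### SAP 5.1 imputes each partial adverse-event date without consulting the event's other recorded date, so an event that ended in the placebo lead-in can count as double-blind and a resolution can precede its onset (minor)

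*SAP*

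**What the plan says.** SAP 5.1 has two onset rules and two resolution rules.

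- **Onset rule (1), day missing.** If "double-blind study medication started during that month then the estimated date is the start date of double-blind study medication". If that medication started in an earlier month, the first of the recorded month is used. If it started in a later month, nothing is imputed and the event is not double-blind treatment-emergent.
- **Onset rule (2), day and month missing.** No date is imputed, but "these AEs will be considered treatment emergent for the double-blind phase and will be included in the double-blind treatment summaries". Such events are left out of the duration calculation.
- **Resolution rule (1), day missing.** If study medication stopped before or during the recorded month, "the estimated date is the last day of the month or the end of the double-blind phase, whichever is earlier". If it stopped later, the last day of the recorded month is used.
- **Resolution rule (2).** "If both the day and the month are missing: the estimated resolution date is the end of the double-blind phase".

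For missing times, the section says to "use time 00:00:00 of the given/imputed date for the start date/time of an AE". SAP 5.2 then decides emergence on the onset: "Any event with a start date and time after the first dose intake will be considered treatment-emergent". Events beginning after the double-blind period are also in scope: "Adverse events with onset date during the withdrawal/follow-up period outside the therapeutic reach of 4 days will be summarized separately".

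**The concern.** None of the four rules looks at the event's other date, and none requires onset to be on or before resolution. A recorded date can therefore be contradicted by an imputed one. This is an error in stated rules, not an absence of detail.

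Two things are at stake. First, a complaint that began and ended while every subject was on lead-in placebo can appear under a treatment arm in the double-blind summaries. SAP 5.2 tabulates treatment-emergent events by arm and study period, so such an event is moved out of the period it belongs to. Second, the end date is capped at the double-blind phase although events are collected to the final visit. Protocol 3.2 gives exploration of withdrawal symptoms as one purpose of the withdrawal period, and that is where end dates can invert. Section 5.1 calls its approach conservative. That can describe counting an event of unknown onset. It does not describe overriding a known date, or shortening an event that outlasted dosing.

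**Working it through.** The plan gives no figure to reproduce. The check applies the rules literally to example records.

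**Inputs.** Lead-in of 3 weeks, double-blind treatment of 6 weeks and withdrawal of 2 weeks (SAP 1.2), with follow-up as late as Day 98 (protocol Time and Events Schedule). I take lead-in as Days 1–21, double-blind as Days 22–63, withdrawal as Days 64–77 and follow-up to Day 98. With lead-in start on 1 March 2018, double-blind start is 22 March, double-blind end 2 May, last dose 16 May and Day 98 is 6 June.

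**Onset side**

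1. Onset year only, resolution recorded as 10 March. The event ended 12 days before the first double-blind dose. Onset rule (2) still counts it as double-blind treatment-emergent.
2. Onset recorded as March, resolution 10 March. Onset rule (1) gives 22 March, 12 days after resolution. Whether the event then counts as double-blind depends on time of day. Its imputed time is 00:00:00, and SAP 2.4 keeps the lead-in open until 1 minute before the first double-blind dose. With a timed dose on 22 March, the event stays in the lead-in. Where SAP 2.4 itself imputes the double-blind start as 0:00, the event falls in the double-blind period. The inverted dates arise either way.

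**Resolution side**

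3. Onset 8 May (withdrawal), resolution recorded as May. Rule (1) gives the earlier of 31 May and 2 May, so 2 May: 6 days before onset. With the month also missing, rule (2) again gives 2 May.
4. Onset 20 April (on treatment), resolution recorded as June. Rule (1) gives the earlier of 30 June and 2 May, so 2 May. Duration is 11 + 2 = 13 days inclusive. The record proves at least 20 April to 1 June: 11 + 31 + 1 = 43 days.

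**If the phase is read as ending on Day 77 (16 May)**

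5. Record 3 becomes 16 May, and the inversion disappears.
6. Onset 20 May (follow-up), resolution recorded as May: the earlier of 31 May and 16 May is 16 May, 4 days before onset. Follow-up onsets still invert.
7. Record 4 becomes 11 + 16 = 27 days, still below 43.

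**Enumeration.** The rules were run over 365 lead-in start dates, every onset day and assumed durations of 0–14 days, with the phase ending on Day 63.

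| Record | Inverted |
|---|---|
| Onset after Day 63, resolution day missing, stop read as last dose (Day 77) | 147,840/153,300 = 96.4% |
| Same, stop read as last double-blind dose (Day 63) | 153,300/153,300 = 100% |
| Onset after Day 63, resolution day and month missing | 153,300/153,300 = 100% |
| Onset in lead-in or double-blind, resolution day, or day and month, missing | 0% |
| Wholly inside lead-in, onset day missing, resolution recorded | 41,790/76,650 = 54.5% |

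The 96.4% falls short of 100% only because some resolutions lie in a month before the stop month, where the cap does not apply. These are shares of date combinations under the assumed durations, not expected event frequencies.

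**The case against.** The strongest reply is that little of this reaches a table. SAP 5.2 counts subjects by organ class and term, severity, relationship and special interest, with emergence decided on onset. It specifies no summary of event duration; duration is mentioned only within 5.1. A reader might infer that the resolution rules distort the adverse-event tables. They do not: inverted or shortened end dates stop at derived dates and durations. That part of the reply stands.

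A second reply concerns terms. SAP 2.4 defines a double-blind treatment period, not a double-blind phase, and protocol 10.1 uses the latter for the span to Day 77. On that reading withdrawal-onset inversions vanish, but follow-up-onset inversions remain, as does shortening of long events. The onset rules are unaffected.

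A third reply is that the records are rare. Lead-in visits are weekly, 5.1 calls for attempts to recover at least the month, and protocol 17.5 provides for queries. This reduces the number of cases without correcting the rule.

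A reader might also gauge the defect by the share of study days after the double-blind phase, or the share of lead-in days in the same month as double-blind start. Neither works. They count calendar days, not events. The first changes with the meaning of the phase and the timing of follow-up. The second includes events with no recorded lead-in resolution, for which the imputation contradicts nothing.

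**Conclusion.** Wrong as written, and minor. Onset rule (2) certainly places an event with a recorded lead-in resolution in the double-blind by-arm summaries. Onset rule (1) certainly can put onset after resolution, but its effect on double-blind status depends on the time rule and the first-dose time, so it should not be cited as certain misclassification. The resolution cap sets resolution before onset for events starting after the phase when the day is missing in or after the month medication stopped, or when day and month are both missing. If the phase ends on Day 77, this is confined to follow-up onsets. It also shortens some on-drug events below what the record proves.

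The documents give no count of partial dates, so no frequency can be stated. A reader might infer a bias in the arm comparison. The documents do not support that: lead-in events precede randomised treatment, so leakage is expected to be non-differential between arms. No effect on a safety conclusion is shown.

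**What to change.** In SAP 5.1:

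1. Impute a missing resolution day as the last day of the recorded month, capped at the date of last contact instead of the double-blind end, and never before onset. With day and month missing, use the date of last contact, kept within the recorded year.
2. State that an event whose recorded resolution precedes the first double-blind dose is not double-blind treatment-emergent, whatever part of the onset is missing, and that an imputed onset may not be later than the recorded resolution.

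In the examples, taking Day 98 (6 June) as last contact, record 3 resolves on 31 May and record 4 on 6 June (11 + 31 + 6 = 48 days). Record 1 leaves the double-blind summaries, and record 2 can no longer have an onset after 10 March.

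The cost is SAP wording and a few lines of code. No new data are needed, and efficacy analyses and clinical management are untouched. The one downside is that some imputed durations become longer.
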